## Study aim

This controlled randomized trial deals with 14+ weeks of intervention with a) bread with gradually reduced salt content, b) combination of salt-reduced bread and dietary counseling in comparison with a control group (bread with standard salt content). Participants will be recruited as families living in the local area of the production bakery in the southwestern part of the Capital Region of Denmark. The study aims to elucidate the metabolic, behavioral and health consequences of reducing salt intake and to explore the effect of different salt reduction strategies among families.

## Motivation for Salt intervention

Excess dietary sodium has a major role in the pathogenesis of hypertension, a leading risk factor for premature death in the world [1,2]. The dietary salt intake in most countries worldwide, including

Denmark, is far beyond the recommended level (<5-6 gram/day) [3] and population-based salt reduction has been rated to be one of the most cost-effective strategies to prevent cardiovascular disease (CVD)[4,5]. A lower salt diet, if continued, may lessen the subsequent rise in blood pressure (BP) with age, which would have major public health implications in terms of preventing the development of hypertension and CVD later in life. In a report developed for the Danish Ministry of Food, Agriculture and Fisheries, we have estimated that a reduction in the mean salt intake of 3 gram/day in the Danish population would reduce fatal and non-fatal cases of CVD by 1,700-2,800 annually and reduce health care costs by up to two billion DKK per year [6]. Much less studies in this area are done among children. However, there is good evidence that salt intake plays an important role in regulating BP in children too [7]. Although the magnitude of the association between salt reduction and blood pressure in children is relatively modest, blood pressure follows a tracking pattern from childhood into adulthood; therefore, the public health benefits of shifting the distribution of population levels is important. Additional consequences of excess salt intake during early life include increased risk of obesity and the development of taste preferences for saltier foods [8].

Several countries including Denmark have initiated national programs to decrease salt intake in the population [9,10]. However, some recent studies have shown a U-shaped association between sodium intake and cardiovascular disease and currently the effect of salt reduction on morbidity and mortality in the population is heavily discussed [9,11,12,13].

In addition to a better understanding of the health effects of a reduced salt intake, there is a need for better evidence regarding effective strategies to reduce salt intake in Denmark and other similar countries. National programs to reduce salt intake on a population-based level relies mainly on food product reformulation as up to 80% of the salt intake in most countries comes from salt added to processed foods [14]. The biggest contributor of dietary sodium intake in Denmark is bread. Therefore, reducing the sodium content in bread could be a relevant part of an effective strategy to reduce the sodium intake of the Danish population. Because sudden large reduction of salt can make foods unacceptable to consumers [15], a gradual reduction of the salt content in small steps is generally recommended [3,16].

To meet the national goal of lowering salt intake by 3 g/d, reformulation of a single food cannot stand alone. Dietary counseling is another possible strategy to reduce salt intake.

All in all, there is a need for high quality studies carried out in "real life settings" over a longer period.

### *Objectives*

The overall aim of this study is to investigate the metabolic, behavioral and health consequences of reducing salt intake and to explore the effect of different salt reduction strategies among families. More specifically the objectives are:

- to examine the effects of two different salt reduction interventions (A. gradually lowering salt content in bread; A+B. intervention combining salt reduced bread and dietary counseling) on the overall dietary intake (including salt), salt-taste sensitivity and preferences
- to examine the (potential adverse) effects of different levels of salt reduction on selected cardiovascular risk factors (blood pressure, blood lipids, renin, aldosterone, noradrenaline, adrenaline, plasma glucose, Hb1AC, anthropometry)
- to explore the mechanisms in the possible association between salt intake, sugar-sweetened soft drink consumption and obesity.

## **Methods**

The project will be carried out at the Center for Clinical Research and Prevention (CCRP), formerly known as *Research Center for Prevention and Health (RCPH)*, '*The Population Surveys in Glostrup*', which has more than 50 years of experience in conducting population surveys. Data collection is scheduled to be completed during the period 1 January 2018 to August 2018 and it is expected that 450 children and adults divided into 120 families will participate.

At baseline and endpoint participants will be examined about salt intake (24 hr urine collection, 7-day dietary record), salt preferences and salt sensitivity, blood pressure, anthropometry, blood lipids, sugar metabolism and hormones. The intervention will last 14+ weeks.

## **Study Design**

STRIVE (Salt Reduction Intervention) is a single blinded, cluster randomized controlled trial, with children and adults recruited as families and randomly assigned to three parallel intervention arms (A: salt reduced bread; A+B: Salt reduced bread and dietary counseling; C: Bread with standard salt content).

Children and parents are targeted as families, to reflect the real life setting that salt is consumed in and because interventions that target the whole family, rather than single participants, are more effective for achieving dietary goals.

For a period of 14+ weeks, bread (rye bread, wheat bread and buns) will be delivered twice a week to the families, either as bread with gradually reduced salt or with a standard salt content.

All families start with a run-in period of bread with standard salt content, which is gradually lowered in intervention group A and A+B during the first month. The bread intervention begins after the baseline health examination (including urine collection and dietary record) has been completed and runs until data from the endpoint study has been collected.

### *Questionnaire*

Information on socio-economic background, general health, smoking habits, physical activity, salt intake and knowledge on diet will be obtained through a short questionnaire. Questions are developed, tested and applied for use in Danish National Surveys

### *Health examination*

Families are invited to attend a health examination at the research center at baseline and at endpoint. At both visits all participants will have a general health examination including measurement of blood pressure, weight, height, and waist circumference as well as semi-fasting blood samples. (No children < 10 years, but children 10 – 17 can volunteer for a blood sample, blood test is compulsory in adults).

Each donor delivers a maximum of 50 milliliters of blood, which corresponds to 1/10 of a normal blood donor loss.

For the testing of microalbuminuria all participant will make a spot urine sample during the health examination day.

Participants (> 10 years) will participate in a salt preference and sensitivity test. Participants are asked to order bread of varying salt content according to their preference. They will also indicate in a line of different salt solutions when they can taste, that the solution is different from water.

Furthermore, participants will collect 24-hour urine 3 days (children only one day) and register their dietary intake during the following 7 days (web-based, estimated portion sizes dietary record) within the week after the health examination both at baseline and at endpoint.

Repeated 24-hour urine collections and 7 days dietary records are chosen, because these methods are the most valid methods to estimate salt intake and the overall dietary intake on an individual level. To verify the completeness of the 24-hour urine collections the PABA (Para-aminobenzoic acid) method is applied in adults.

#### *Urine Collection*

Participants will receive materials for three 24hr urine collection; a brown bottle (3 L), a smaller 'visiting bottle' (0.5L), a safety pin for attachment to a suitable place as a reminder. Each family will receive a large backup bottle (5L) as a backup, a funnel and a urinary hat for the toilet, to aid urine collection. Adults are given three urine monovettes per day and children two for collection of urine aliquots after the completion of each 24 hr collection period. A pen to mark containers and monovettes with name, day and volume.

For validation adults are given 3\*3 80mg PABA tablets (Glostrup Hospital Pharmacy).

Participants will also receive a form to register beginning and ending of the collection periods, PABA administration and exceptions to the protocol (ie estimation of urine loss, medicine).

Adults will be instructed to collect 24 h urine for three consecutive days (1 weekend day, 2 working days) and children for 1 day (weekend day).

#### *Seven-day web-based dietary record*

All participants must record their dietary intake for seven days at baseline and at endpoint using a web-based dietary record system. Each of the seven days participants will be guided through the meals of the days and asked to indicate the food consumed as well as the portion size based on images. Participants will receive verbal and written instructions in the use of the web-based system as well as a link to a video instruction. Parents will assist the registration of their children. Reminders will be send, if the record hasn't been completed the day before.

#### *Biochemical analyses*

In the blood samples, biomarkers are determined for fat metabolism (total cholesterol, HDL, LDL, triglycerides), sugar metabolism (plasma glucose, and HbA1C), hormones (aldosterone, renin, adrenaline and noradrenaline).

Urine samples will be analyzed for creatinine, sodium, potassium and in spot urine albumin will also be determined. These biomarkers are continuously analyzed at the Clinical Biochemistry Department at Rigshospitalet, Glostrup.

In addition to the above, biological material (urine, serum / plasma and whole blood) is stored for later research. The biological material is stored for up to 50 years (31 December 2068) after which the material is destroyed.

The purpose of the research biobank is to secure biological material for future research. The material will be unique as it represents representative samples of the population. This ensures a preparedness for public health research in the future. Participants provide informed written consent for the storage of biological material in research biobank. When a future research project wishes to use the biobank for purposes not covered by this protocol, the investigators shall ensure the retrieval of informed consent or seek exemption from this requirement by the Scientific Ethics Committee.

### Dietary counselling

Participants in intervention group B will receive dietary counselling on top of salt reduced bread, to further reduce dietary salt and increase potassium. The group-based tuition will include official guidelines on salt and healthy diet (especially fruit and vegetables rich in potassium). Hereafter families will be invited to an individual meeting setting goals for reducing sodium and increasing potassium. To reinforce compliance families will receive weekly newsletters and two telephone calls.

### Participants and Recruitment procedures

In January – February 2018 families will be recruited through digital and paper advertisements posted in social media, schools, kindergartens and companies sited in five municipalities (Albertslund, Ballerup, Egedal, Glostrup and Rødvore) in the southwestern part of the Capital Region of Denmark. The area is selected to be close to either Smørum Konditori, the baker that produces the intervention bread, or the research center (Center for Clinical Research and Prevention, Glostrup Hospital), where the health examinations will take place.

Families are defined as minimum one child and one parent living together. Children, who lives fifty percent of their time with each of their divorced parents, will be able to participate if both parents join the study. Participants will be screened to identify participants living with children between 3 and 17 years and with a daily intake of both white and/ or brown bread (> 175 gram of bread/day). Exclusion criteria are: antihypertensive and lipid-lowering treatment, pregnancy, diabetes, coronary heart disease, urine albumin greater than 300 mg/day.

At the end of the baseline health examination families will be systematically randomized by a computer into one of the three groups. In divorced families, both parents (and their families) will follow the randomization of the parent first examined.

### Publication of experimental results

Both "negative" and "positive" as well as inconclusive results will be published in scientific journals under the Vancouver rules.

Official title of the study: Salt Reduction InterVENTion: Examination of the metabolic, behavioral and health consequences of reducing salt intake. A randomized controlled trial in a real life setting.

NCT number: Not yet assigned

Date of the document: November 30, 2018

Statistical analysis plan STRIVE

Statistical Analysis Plan STRIVE

We are currently writing up a more in-depth plan of the statistical analysis plan, which will be uploaded when ready.

Aim: The Salt Reduction InterVENTion (STRIVE) aims to investigate the metabolic, behavioral and health effects of 14+ weeks of gradually salt reduced bread alone or in combination with dietary counselling compared to families receiving standard bread.

Design: Randomised, controlled trial with three parallel arms

Methods: Eligible families will be randomly allocated into three groups to investigate the effect of different salt reduction strategies: **A:** salt reduced bread; **A+B:** Salt reduced bread and dietary counseling; **C:** Bread with standard salt content. Participants will be instructed to replace their usual consumption of bread by bread products provided in the study. The primary outcome is changes in sodium intake measured by 24 hr urine excretion. Secondary outcomes are change in potassium and Sodium/ Potassium ratio, blood pressure, blood lipids, salt-taste sensitivity and renin, aldosterone and sympathetic nervous response. Participants will be examined before and by the end of the intervention. The flow of the trial is shown in figure. 1.

Sample size

The average daily intake of bread in Denmark is 139 grams (123 gram for children. One of the inclusion criteria is a daily intake of bread of 175 gram among adults. The average salt content of bread in Denmark is 1.3 gram/100-gram bread. Thus, the average daily intake of salt from bread among the participants is estimated to be approximately 2.3 gram. The expected reduction in salt intake due to the salt-reduced-bread intervention (average reduction of 55%) is 1.25 gram per day. The expected salt reduction in the intervention group with the combined intervention is on average 3 gram (based on the current average daily salt intake and the target for the intervention). The statistical power calculations were based on data from a population-based study at Center for Clinical Research and Prevention, DK (CCRP) showing an average daily intake of salt of 8.3 gram (SD 2.2). The analyses were done to fit the cluster-randomized design and showed that if the true difference in the intervention and control means after intervention is 1.2 gram per day we will need to include 50 subjects in each of the three groups to be able to reject the null hypothesis at a 5% level and with probability (power) 0.8. The intra-class correlation within families was assumed to be 0.33 and the average family was assumed to consist of four members. With an expected difference in salt intake of 1.2 gram/day we will expect to see clinical relevant differences in blood pressure, blood lipids, renin, aldosterone and albuminuria.

Randomization, allocation and concealment

Once included, baseline assessments will be conducted before the families will be randomized (1:1:1) to three groups (salt reduced bread, salt reduced bread and dietary counseling, standard bread no dietary counseling), using simple randomization.

A *data manager*, who has no other involvement in the trial than producing the data application will produce a computer-generated sequence of random group assignments (allocation sequence). *Participants* will be blinded to the treatment they receive. Bread will be coded by a red or blue label, and families collect

bread according to the color of their group. The color code will be known by two *bakers* responsible for baking the bread but blinded to the rest of the *bakery staff*, including those handing out the bread to the

[figure not shown]

Figure 1. Trial flow diagram. *Participants are recruited as families, screened for eligibility, informed about the trial. After informed content, baseline visit completed ending with allocation to trial group. Then dietary*

record and urine collection, while eating own bread before intervention start. Four months later endpoint visit followed by 7-day-dietary record and 3-day urine collection while consuming intervention bread.

participants. Color-code for the bread will be revealed after the final participant has completed the second health examination.

The *secretary* screening and enrolling the participants will be blinded with respect to group allocation. The three *research nurses* conducting the clinical measurements, at baseline (before randomization) and at endpoint measurement will remain blinded to the group allocation. Given the nature of the intervention it is not possible to blind the *nutritionists* delivering the dietary counselling. Biochemical analyses will be carried out by *laboratories* blinded to the allocation of the samples. Thus, the primary outcome measures will be blinded to the outcome assessors.

Data management

The data will be handled in accordance with the rules from the Danish Data Protection Agency. All data will be entered blinded, with error control in the application or using double entry. Data entry will be validated by checks for valid values and range checks. For the analyses data will be exported to SAS Enterprise Guide 9.4, SAS institute, Inc., Cary, NC, USA: The electronic database and analyses will be stored on a secure computer server with personal login access authorized by the primary investigator.

Recruitment and withdrawals

Recruitment rates and numbers of withdrawals and dropouts will be reported along with reasons for exclusions, dropouts and withdrawals.

Compliance

To follow participants compliance with the intervention, bakers will inform the research team if bread is not being picked up. Families will fill in forms on bread consumption on a weekly basis.

Families receiving dietary counselling will be interviewed twice on their adherence to their own salt reducing goals.

Urine collections will be checked for completeness by the creatine and PABA method.

Table 1. Outcome variables and assessment tools

Assessment	Outcome	Method
Inclusion / Exclusion	Family structure, Bread consumption, Gluten intolerance Pregnancy, Diabetes, Hypertension	Screening questionnaire, Telephone interview, Interview by nurse
Informed consent		Written, Intro meeting Informed by nurse
Demographics	Gender, age, family, marital status, education, work	Questionnaire
Lifestyle	Physical activity, smoking, alcohol, salt and bread consumption, food habits	Questionnaire

Medical history	Hypertension, heart disease, cancer, diabetes, cholesterol, coeliac disease	Questionnaire, Interview
Anthropometry	Height, weight, BMI, arm and waist circumferences, fat percentage	Standardized measurements by nurse, impedance
Blood pressure	Pulse, diastolic BP Systolic BP	Average of three resting BP's, 5 min rest
Biochemistry	P-glucose, HbA1C, Triglyceride, Cholesterol, HDL, LDL, renin, aldosterone, adrenalin, noradrenalin, U-albumin, U-sodium, U-potassium, U Creatinine, U-albumin	Semi fasting (min 2 hr) blood samples after 30 min rest, spot urine, micral test
Salt preference/ sensitivity	Preference bread 0.4/0.8/1.2 g salt/ 100 g Recognition sweet, salt	Taste of bread Taste of sugar and salt solutions
24 hr urine collection	U-sodium, U-potassium, U Creatinine, PABA	Adults: 3 days, 24 hr urine + PABA Children: 1 day 24 hr urine
7 Day dietary history	Energy, macro- and micronutrients, foods, meal pattern, eating at home/ out	Web-based dietary record, estimated portion sizes from photos
Bread intervention	Bread collection twice a week and weekly response to questionnaire on consumption Weekly test of salt content in bread Participants evaluation of bread consumed	14+ weeks of bread intervention. Six weeks gradual reduction in salt. Intro week 1-2 after completion first dietary record and urine collection End after completion final dietary record and urine collection.
Randomization	Systematically into three groups	By allocation sequence
Dietary counseling	Salt intake, potassium Motivation, barriers, focus points Actions applied to reduce salt intake	Salt screening questionnaire, interview, follow up telephone interviews Evaluation questionnaire

Statistical analysis

Table 1 lists the outcome variables and assessment tools. The *primary study outcome* is the change in 24-h sodium (mean of 3 collections in adults, 1 collection in children). *Secondary outcomes* are change in potassium and Sodium/ Potassium ratio, blood pressure, blood lipids, salt-taste sensitivity and renin, aldosterone and sympathetic nervous response.

Baseline data will be presented as means (std) or medians (with range) for continuous data depending on the distribution of the variable. Categorical variables will be presented as frequencies and percentages.

Estimation of treatment effect for the primary outcome will be calculated using an “intention to treat” analysis, including all randomized participants regardless of the adherence to the intervention and dropouts. To create a full analysis data set, missing data for the primary outcome will be imputed using multiple imputation with 100 samples. A linear mixed model with change in sodium excretion as outcome variable, treatment group and baseline sodium excretion as fixed effects, and family ID as random effect.

The estimates or the size of treatment effects will be presented along with 95% confidence intervals and actual p-values. Levels of significance will be set at 0.05. The primary analysis will be unadjusted.

To account for differences in the adherence to the bread intervention, a per-protocol linear mixed model analysis will be undertaken following the principles outlined above.

Linear mixed models will also be applied to the analyses of the secondary outcomes.

Further analyses will be described in the statistical analysis plan, which we are currently writing up.

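### The 1.2 g/day difference used for power comes from an adult bread criterion and is unsupported for a primary analysis that pools children; separately, 50 per group does not give 80% power even at 1.2 g

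*SAP*

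**What the plan says.** The SAP's sample size section builds the expected effect from bread intake. It gives "The average daily intake of bread in Denmark is 139 grams (123 gram for children", then "One of the inclusion criteria is a daily intake of bread of 175 gram among adults", then "The average salt content of bread in Denmark is 1.3 gram/100-gram bread". From these it estimates about 2.3 g of salt per day from bread for the participants as a whole, without separating adults from children, and concludes: "The expected reduction in salt intake due to the salt-reduced-bread intervention (average reduction of 55%) is 1.25 gram per day".

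The power statement is conditional. It says that "if the true difference in the intervention and control means after intervention is 1.2 gram per day", then "we will need to include 50 subjects in each of the three groups" for 80% power at the 5% level. The inputs are an SD of 2.2 g, an intra-family correlation of 0.33 and an average family of four, and the calculation is described as fitted to the cluster design.

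The SAP's statistical analysis section defines the primary outcome as change in 24-hour sodium ("mean of 3 collections in adults, 1 collection in children"). All randomised participants enter one linear mixed model with treatment group, baseline sodium and a family random effect. There is no term for age group.

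The protocol's recruitment section gives the bread criterion as "with a daily intake of both white and/ or brown bread (> 175 gram of bread/day" and does not limit it to adults. It requires at least one child and one parent per family. Its methods section expects 450 people in 120 families, which is 150 people per arm.

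**The concern.** The planning difference for salt-reduced bread (arm A) against control (arm C) should describe the people in the primary analysis. Here it rests on an intake that the SAP assigns to adults. The lower intake that the SAP quotes for children is printed beside it but not used. Families of four are assumed, so children clearly count towards the sample.

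If children eat less bread, the same percentage cut removes less salt, and the pooled difference is smaller than the adult one. The SAP also uses 1.2 g to justify expecting relevant differences in blood pressure, lipids, renin, aldosterone and albuminuria.

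The stated 50 per group raises a second, independent question: whether it follows from the inputs printed with it. If the sponsor corrected only the clustering, the margin at the expected enrolment would still rest on an unsupported 1.2 g.

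**Working it through.** **Inputs.** From the SAP sample size section: 175 g (adults), 123 g (children), 139 g (overall average), 1.3 g salt per 100 g, 55% reduction, SD 2.2, ICC 0.33, family size 4, 80% power, 5% level. From the protocol's methods: 450 / 3 = 150 per arm. Assumed here because not stated: a two-sided test, no dropout, no gain from baseline adjustment, the same SD for children, and the share of children.

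**Step 1, the plan's effect.** 175 × 0.013 = 2.275 g, and 2.275 × 0.55 = 1.251 g. This reproduces the 2.3 g and the 1.25 g.

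**Step 2, the same formula for children.** 123 × 0.013 × 0.55 = 0.879 g.

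**Step 3, the plan's sample size.**
- Formula: n per group = 2 × (SD × (1.960 + 0.842) / d)² × DE, with DE = 1 + (4 − 1) × 0.33 = 1.99.
- At d = 1.2 without clustering: 2 × (2.2 × 2.802 / 1.2)² = 52.8, so 53.
- With clustering: 52.8 × 1.99 = 105.0. Rounding to 53 first gives 53 × 1.99 = 105.5, so 106.
- Power of 50 at 1.2 g: 78% without clustering. With clustering the standard error is 2.2 × √(2 × 1.99 / 50) = 0.621, the ratio is 1.2 / 0.621 = 1.93, and power is about 49%.
- One-sided testing gives 42 without and 84 with clustering. Using d = 1.25 and no design effect gives 49, which is close to the stated 50 but leaves out the clustering that the SAP says was included.

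**Step 4, pooled difference.** With child share w, d = w × 0.879 + (1 − w) × 1.251. It falls below 1.2 g once w exceeds (1.251 − 1.2) / (1.251 − 0.879) = 14%. With at least one child and one parent per family and four members on average, w lies between about 25% and 75%.

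| Child share | Pooled d (g) | n per group for 80% | Power at 150 per group |
|---|---|---|---|
| 25% | 1.16 | 113 | 90% |
| 50% | 1.07 | 134 | 84% |
| 75% | 0.97 | 160 | 77% |

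All rows use SD 2.2 and DE 1.99. At 1.2 g, power at 150 per group is 92%.

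**Step 5, what would restore 1.2 g (half children).**
- A pooled 1.2 g needs a mean intake of 1.2 / (0.013 × 0.55) = 167.8 g. With children at 123 g, adults must average 2 × 167.8 − 123 = 213 g.
- If children in selected families exceed the national figure in proportion, 175 × 123 / 139 = 155 g. Their reduction is then 1.11 g, the pooled value (1.25 + 1.11) / 2 = 1.18 g, and power at 150 per group 91%.
- An overall SD of 2.2 × 1.065 / 1.2 = 1.95 would keep the same standardised effect as 1.2 / 2.2.

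**The case against.** The SAP's power sentence is conditional on a true difference of 1.2 g, so doubt about 1.2 g does not make it false. That stands: the first part of this point concerns the support for an assumption.

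The 0.88 g and 1.07 g also mix unlike quantities. The 175 g is an entry minimum, so the adult mean should lie above it. The 123 g is a national child mean, and families chosen for high bread intake may have children who eat more. The child share and child SD are not given. A smaller SD in children could cancel the loss, while a single urine collection instead of three could add to it. All of this stands, and Step 5 shows that modest shifts bring the pooled value back to about 1.2 g.

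The primary model adjusts for baseline sodium, which normally reduces variance. At an assumed baseline correlation of 0.5, 150 per group at 1.07 g would have about 93% power. For the stated 50, an assumed correlation of 0.5 gives a clustered requirement of 80 and one of 0.7 gives 54. Baseline adjustment could therefore come near 50 only with a high correlation that the SAP neither states nor says it used.

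A reader might infer that the stated power is overstated by a known amount on the plan's own numbers, or that the trial is too small. The documents support neither. They do not fix the pooled difference, and the expected 150 per arm exceeds the cluster-adjusted requirement at 1.2 g and at half children. Nor does the point extend to the combined arm, whose 3 g expectation is not built from the 175 g.

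**Conclusion.** Two things hold.

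First, the 1.2 g difference between arms A and C has no child component and is unsupported for the pooled population. On the quoted intakes it would be about 1.16, 1.07 or 0.97 g for 25%, 50% or 75% children. These values depend on adults averaging exactly 175 g and children 123 g, so they are a sensitivity range and not a corrected estimate.

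Second, and independently, the stated 50 per group does not follow from its own inputs: 80% power at 1.2 g needs 53 without clustering and about 105 to 106 with it. Under clustering this gap is the larger one. It takes power at 50 per group to about 49%, and half children would lower it further to about 40%.

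The practical effect at the expected enrolment is a smaller margin. Without dropout, 150 per group keeps at least 80% power with 25% or 50% children and falls to about 77% with 75%. Treating dropout as lost sample, the tolerable loss is about 29% at 1.2 g (1 − 106/150) but about 11% at half children (1 − 134/150).

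The two documents also differ on whether the 175 g criterion is limited to adults, and this bears directly on whether 175 g can stand for all participants.

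**What to change.** In the SAP's sample size section:

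1. Replace 50 per group with the cluster-adjusted requirement, about 106 at 1.2 g, and state whether the test is two-sided.
2. State the assumed adult, child and pooled differences for arm A against arm C, the child share and the SD, with the basis for each. Give the requirement as a range, for example about 113, 134 or 160 per group for 25%, 50% or 75% children.
3. Give the power of the expected 150 per group under the same shares, about 90%, 84% or 77%, instead of relying on the 92% that 1.2 g implies. State the conditions: SD 2.2, design effect 1.99, two-sided 5%, no dropout, no gain from baseline adjustment. If the sponsor has data on intake in bread-eating families, a child SD or a baseline correlation, those should replace the illustrative values.
4. Reconcile the bread criterion between the protocol's recruitment section (not limited to adults) and the SAP (adults).

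The SAP says that a fuller plan is being written, so these changes can go there. The cost is wording only: the stated figures become less favourable, and no extra enrolment is proposed.
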